5.5.6. Dose Modification of Lenalidomide during a Cycle (applies to Days 1-21)

The dose of lenalidomide should be modified according to the dose modification guidelines in Table 6 if any of the following toxicities occur:

Table 6: Dose Modification or Interruption for Lenalidomide Toxicity during a Cycle

Toxicity	Intervention
Thrombocytopenia:	
 Grade 3 (decrease to <50,000/μL) associated with Grade ≥ 2 bleeding, OR Grade 4 (decrease to <25,000/μL) 
 Interrupt lenalidomide treatment for the remainder of the cycle Reduce the dose of lenalidomide by one dose level (5 mg) at the start of the next cycle. Do not initiate a new cycle until the subject meets cycle initiation criteria (see Section 5.5.5). Do not dose below 5 mg daily.
Neutropenia:	
 ANC <1,000/μL for > 7 days, OR ANC <1,000/μL with an associated temperature $\geq 38.5^{\circ}\text{C}$, OR ANC <500/$\mu$L 
 Interrupt lenalidomide treatment for the remainder of the cycle Reduce the dose of lenalidomide by one dose level (5 mg) at the start of the next cycle. Do not initiate a new cycle until the subject meets cycle initiation criteria (see Section 5.5.5). Do not dose below 5 mg daily.
Rash:	
 Any Grade desquamating (blistering) Grade 4 non-blistering Grade ≥ 3 
 For any Grade desquamating or Grade 4, discontinue lenalidomide permanently For Grade ≥ 3 rash, hold lenalidomide until rash improves to \leq Grade 1, then resume at original dose (for first episode) or lower dose as clinically indicated. Treatment with 20 mg prednisone PO or equivalent daily for 10 days (with or without taper) and/or antihistamines PO daily is recommended; discontinue allopurinol if rash is thought to be at least possibly related to allopurinol. During DLT observation period: If \geq Grade 3 rash has not improved to at least Grade 1 within 10 days using a temporary hold of study drugs and administration of up to 100 mg of prednisone or equivalent (with or without taper) and/or antihistamines daily, rash is considered a DLT. Outside of DLT observation period: see recommendations for Grade ≥ 3 rash above
Venous thromboembolism Grade ≥ 3	
 Interrupt lenalidomide treatment for the remainder of the cycle Initiate therapeutic anticoagulation – see Section 6.1.2.3. Resume lenalidomide without dose modification at the start of the next cycle if the benefit of therapy on this study outweighs the risk for bleeding.
Hyperthyroidism or hypothyroidism	
 Interrupt lenalidomide treatment for the remainder of the cycle

Toxicity	Intervention
	
 • Evaluate etiology and initiate appropriate therapy • Reduce the dose of lenalidomide by one dose level (5 mg) at the start of the next cycle. Do not initiate a new cycle until the subject meets cycle initiation criteria (see Section 5.5.5). Do not dose below 5 mg daily.
Creatinine Clearance \leq 60 mL/min (Cockcroft-Gault or 24-hour creatinine clearance collection)	
 • Interrupt lenalidomide treatment for the remainder of the cycle • Reduce the dose of lenalidomide according to the recommendations below based upon creatinine clearance at the start of the next cycle. Do not initiate a new cycle until the patient meets cycle initiation criteria (see Section 5.5.5). Do not dose below 5 mg daily. 
 ○ CrCl 30-60 mL/min: 
 – If the dose for subjects with CrCl >60 mL/min is 25 or 20 mg of lenalidomide, the starting dose is 10 mg every 24 hours. – If the dose for subjects with CrCl >60 mL/min is 15 or 10 mg of lenalidomide, the starting dose is 5 mg. ○ CrCl <30 mL/min (not requiring dialysis): 15 mg every 48 hours • At Investigator discretion, subjects started with a reduced lenalidomide dose due to baseline CrCl \geq30mL/min but <60mL/min may have the lenalidomide dose gradually increased in a step-wise manner at the start of Cycle 2 or at the start of subsequent treatment cycles, if they tolerated the prior treatment cycle without requiring dose modifications, dose interruptions or delays due to toxicity. Lenalidomide dose titrations are permitted in 5 mg increments on the same dosing schedule up to the maximum allowable target dose. • The lenalidomide dose may only be increased once every 28 days (or less frequently), and may only be increased if the prior treatment cycle was completed without requiring dose modifications, interruptions or delays due to toxicity. • If creatinine clearance becomes >60mL/min for a minimum of 2 cycles then one may re-escalate to the dose prior to reduction for renal dysfunction at the discretion of the Investigator.
Any other Grade 3/4 non-hematologic toxicities attributed to lenalidomide	
 • Interrupt lenalidomide treatment for the remainder of the cycle. • Reduce the dose of lenalidomide by one dose level (5 mg) at the start of the next cycle. Do not initiate a new cycle until the patient meets cycle initiation criteria (see Section 5.5.5). Do not dose below 5 mg daily.

Table 7: Dose Reduction of Lenalidomide

Current Dose Level	10 mg	15 mg	20 mg	25 mg
Dose Reduction 1	5 mg	10 mg	15 mg	20 mg
Dose Reduction 2	Discontinue	5 mg	10 mg	15 mg
Dose Reduction 3	NA	Discontinue	5 mg	10 mg
Dose Reduction 4	NA	NA	Discontinue	5 mg
Dose Reduction 5	NA	NA	NA	Discontinue

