1.13.3. Rationale for Changes in Amendment 2.0

Potential re-escalation to higher doses of lenalidomide after confirmation of safety in Cohort -1 (de-escalation cohort) was included in Protocol Amendment 2.0 to enable a higher and potentially more efficacious dose of lenalidomide for the Phase 2 portion of the study.

Based on the findings in the CTEP/A051103 study and the findings in Cohort 1 at Dose Level 1, the DLT rules for rash were modified in this amendment. In both studies, rash was being reported frequently mostly early in the treatment period (during the DLT observation period [Cycle 1]), the cases were clinically manageable, no cytokine storm reactions were seen, and re-treatment after a drug hold was clinically permissible if allowed. Thus, higher and potentially more efficacious doses of lenalidomide will be explored in this study.

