5.5.5. Dose Delay, Reduction or Discontinuation of Lenalidomide

In order to initiate a new cycle of therapy with lenalidomide, the subject must have an ANC $\geq 1,000/\mu\text{L}$ and a platelet count $\geq 50,000/\mu\text{L}$ and no lenalidomide related Grade ≥ 3 toxicity on Day 1. If these two criteria are not met, the entire cycle with all drugs is to be delayed and a repeat assessment is to be performed per the Investigator's decision. The initiation of lenalidomide should be delayed until the subject meets the above criteria at which time the subject will initiate drug without dose modification. The initiation of lenalidomide may occur on any day of the cycle, but missed doses must be omitted. Omitted doses should not be made up, and lenalidomide dosing must end no later than Day 21 of any given cycle. Once a cycle has initiated, if lenalidomide must be held for toxicity during dosing, except for an AE of rash, lenalidomide will not resume until Day 1 of the subsequent cycle, provided the subject meets the cycle initiation criteria above, with dose adjustments as per [Table 6](#).

Treatment with lenalidomide should be withheld for any unmanageable, potentially study drug-related non-hematological toxicity that is Grade 3 or higher in severity and any hematologic toxicity as described in [Table 6](#). In the event the subject is diagnosed with a thyroid condition or experiences a drop in creatinine clearance to $\leq 60 \text{ mL/min}$, refer to [Table 6](#) for further instructions.

Any other clinically important events where dose delays may be considered appropriate by the Investigator must be discussed with the Medical Monitor.

Lenalidomide may be withheld for a maximum of 28 consecutive days for toxicity. Lenalidomide treatment should be discontinued in the event of a lenalidomide related toxicity lasting more than 28 days, unless approved by the Medical Monitor.

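### In Table 6 the hold-and-resume rule for lenalidomide is worded to include Grade 4 rash, which the preceding bullet stops permanently, and the row's DLT sentence is wider than Section 5.2

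*Protocol*

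**What the plan says.** The rash row of Table 6 (Protocol Section 5.5.6) has four instructions for lenalidomide.

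1. Permanent stop: "For any Grade desquamating or Grade 4, discontinue lenalidomide permanently".
2. Hold and resume, for rash of Grade 3 or higher: hold until the rash is Grade 1 or lower, "then resume at original dose (for first episode) or lower dose as clinically indicated".
3. DLT sentence: within the DLT observation period, rash of Grade 3 or higher that has not improved to Grade 1 within 10 days, with drugs held and steroids and/or antihistamines given, counts as a DLT.
4. Closing line: "Outside of DLT observation period: see recommendations for Grade" 3-or-higher rash, above.

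The DLT definition itself is in Section 5.2. There, any non-hematologic event of Grade 3 or higher that is possibly related to study drug is a DLT, subject to listed clarifications. The rash clarification, with its 10-day improvement test, is given for Grade 3 only. The DLT paragraph of Section 5.4.3 also says Grade 3.

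**The concern.** A reader who looks up Grade 4 rash finds it named in the first instruction and included in the range of the second. Stopping for good and resuming after recovery cannot both be followed. The second instruction has no word such as *other* or *except*. The closing line, which governs every cycle after the Phase 1b DLT window and all of Phase 2, refers to the second instruction and not the first.

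At stake is whether lenalidomide may be restarted after a life-threatening rash. The DLT sentence raises a separate question: whether a Grade 4 rash in Cycle 1 of Phase 1b that settles within 10 days counts as a DLT. Phase 2 is planned for up to 70 international centers and about 55 subjects (Section 3.3), so many sites would apply the table with little or no experience of it.

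**Working it through.** No arithmetic decides this point. The check compares which rashes fall under each instruction, then looks for a rule of precedence.

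**Step 1. Coverage of the two lenalidomide instructions, as worded.**

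| Rash | Permanent stop | Hold and resume |
|---|---|---|
| Grade 3, not desquamating | no | yes |
| Grade 4, not desquamating | yes | yes |
| Grade 1–2, desquamating | yes | no |
| Grade 3, desquamating | yes | yes, but see step 2 |
| Grade 4, desquamating | yes | yes, but see step 2 |

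The clear overlap is non-desquamating Grade 4 rash.

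**Step 2. Does the table layout explain it?** The toxicity cell lost its line breaks in extraction and runs "Any Grade desquamating (blistering) Grade 4 non-blistering Grade" 3 or higher. If its last entry is non-blistering rash of Grade 3 or higher, the trigger for holding excludes desquamating rash, and the overlap for desquamating rash largely disappears. Non-blistering Grade 4 rash is still inside that entry. The Grade 4 overlap also lies in complete sentences of the intervention column, so it does not depend on the cell's layout.

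**Step 3. Is there a rule of precedence elsewhere?**

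- Section 5.5.5 says to withhold lenalidomide for unmanageable, possibly drug-related non-hematologic toxicity of Grade 3 or higher. It does not separate Grade 4 rash.
- Section 5.4.3 (ibrutinib) sends the reader to Table 6 for lenalidomide and rash. Section 6.1.1 sends the reader to Sections 5.4.3 and 5.5.6.
- Section 6.1.3 deals only with how long steroids may be given for rash.
- Section 9.2 does not name Grade 4 rash among the reasons to stop treatment.

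None settles the order. The same table does mark a residual category where one is meant: its last row begins "Any other Grade 3/4 non-hematologic toxicities attributed to lenalidomide".

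**Step 4. The DLT sentence against the DLT definition.**

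| Place | Rash to which the 10-day test applies | Grade 4 rash, possibly related, improved to Grade 1 within 10 days |
|---|---|---|
| Section 5.2 | Grade 3 | DLT, because no clarification covers it |
| Section 5.4.3, DLT paragraph | Grade 3 | Not addressed |
| Table 6, rash row | Grade 3 or higher | Not a DLT, by implication |

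The Table 6 sentence states only when rash is a DLT, so the last entry is an implication. It is nevertheless how the 10-day test works for Grade 3 in Section 5.2. The DLT count drives expansion and escalation under Section 5.1, so the two places should agree.

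**Step 5. How often could it arise?** In the cited three-drug follicular lymphoma study (Section 1.13.2), 8 of 22 subjects had Grade 1 or 2 rash and 8 had Grade 3. That is 8 + 8 = 16 with rash, leaving 22 − 16 = 6 with none listed, and no Grade 4 is listed. The DLT-qualifying events listed for this trial in Section 1.14.4 include two Grade 3 rashes and no Grade 4 rash. The Phase 1b safety summary in Section 1.17.1 is not visible in the text reviewed.

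**The case against.** The strongest reply is that ordinary reading resolves the overlap. The permanent-stop bullet comes first, is stricter, and names Grade 4. If the hold-and-resume bullet governed Grade 4, naming Grade 4 in the first bullet would have no effect. The only reading that gives both bullets work to do is a permanent stop for Grade 4 or desquamating rash and a hold for the rest. This is right as to intent, and it is why the point is minor. It remains an inference, and the closing line points the other way.

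Safeguards also limit harm. A life-threatening event is serious (Section 11.1.2) and must reach the sponsor within 24 hours (Section 11.2.2.2). In the Phase 1b window, continuing after a DLT requires expected benefit, manageable toxicity and notice to the sponsor (Section 5.1). These make an unnoticed restart unlikely but do not correct the row.

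A reader might infer two stronger claims, and the documents support neither.

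- *The protocol favors re-treatment after Grade 4 rash.* Section 1.13.3 does say that "the cases were clinically manageable, no cytokine storm reactions were seen, and re-treatment after a drug hold was clinically permissible if allowed". But it is explaining a change to the DLT rules on the basis of cases already seen, and the highest rash grade listed in Sections 1.13.2 and 1.14.4 is Grade 3.
- *The protocol permits restart within the same cycle after Grade 4 rash.* Section 5.5.5 does say that, "except for an AE of rash, lenalidomide will not resume until Day 1 of the subsequent cycle". That exemption concerns a drug being held. A drug stopped permanently is not being held, so the argument assumes the reading in dispute.

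**Conclusion.** The point holds as a minor internal inconsistency in a safety rule. As written, Grade 4 rash falls under both a permanent stop and a hold-and-resume instruction for lenalidomide, and no section states which prevails. The permanent stop is almost certainly intended. The overlap for desquamating rash is less certain because of the damaged toxicity cell, and the conclusion does not rest on it.

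The mismatch in the DLT sentence is a separate and substantive part of the point. Section 5.2 is the formal definition, and under it a possibly related Grade 4 rash is a DLT whether or not it improves within 10 days.

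The number of subjects affected is probably small and cannot be estimated from the visible text. Carrying a rate over from the 22 follicular lymphoma subjects would be unsound: it is a different disease, some dose levels used 420 mg of ibrutinib, and none exceeded 20 mg of lenalidomide. An affected subject would also have to recover to Grade 1 or lower and be treated by an investigator who chose the less cautious bullet. The ORR test and the sample size are unaffected. Nor should this be read as a flaw in the trial's design, since the intended rule is sound and only its wording is at fault.

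**What to change.** In the rash row of Table 6:

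1. Keep the permanent-stop bullet as it is.
2. Limit the hold-and-resume bullet to *Grade 3 non-desquamating rash*, and align the toxicity cell if needed.
3. Change the DLT sentence from Grade 3 or higher to *Grade 3*, to match Section 5.2 and the DLT paragraph of Section 5.4.3.
4. Change the closing line to *see recommendations above*, so that it includes the permanent stop.

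The cost is a few words in one table row, which can go into the next amendment. Sample size, schedule and analysis do not change.

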1.17. PCYC-1123-CA Phase 1b Data Summary

As of 25 April 2016, a total of 38 subjects were enrolled (37 treated) in Cohort 1 (13 subjects enrolled, 12 treated), Cohort -1 (7 subjects enrolled), Cohort 1+ (9 subjects enrolled) and Cohort 2 (9 subjects enrolled).

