1.17.2. DLRC Meeting Outcome

Safety and preliminary efficacy data for all enrolled cohorts were reviewed by the DLRC on 25 April 2016. The voting members (e.g. medical monitors, participating Investigators, safety officer, and biostatistician) present during the call and 4 Investigators who voted per e-mail unanimously voted to continue the study in Phase 1b with Cohort 3 (dose level of 25 mg of lenalidomide in combination with ibrutinib and rituximab) and to repeat safety assessments. In addition, the voting members unanimously voted to proceed to Phase 2 with the dose of 20 mg of

lenalidomide in parallel with Cohort 3 (25 mg lenalidomide) in the Phase 1b. Based on the DLRC recommendation, the Sponsor (Pharmacyclics LLC) is planning to proceed with the 25 mg lenalidomide dose level in the Phase 1b of the study. In parallel, the Sponsor is planning to proceed with the Phase 2 portion of the study with the recommended Phase 2 dose of 20 mg lenalidomide, which is the same or similar recommended Phase 2 dose level tested in other trials using ibrutinib, lenalidomide and rituximab (Ujjani et al ASH 2015, NCT02160015 [15 and 20 mg lenalidomide]; NCT02532257 [15 and 20 mg lenalidomide], NCT02446236 [10-25 mg lenalidomide], NCT02636322 [25 mg lenalidomide]; Wilson et al ASH 2015, NCT02142049 [15, 20 and 25 mg lenalidomide].

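### Protocol Table 6 gives a single lenalidomide dose for CrCl <30 mL/min, which is higher than the CrCl 30-60 dose for subjects assigned 15 or 10 mg and higher than the current dose of anyone already on 5 mg daily

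*Protocol*

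**What the plan says.** Protocol Section 5.5.5 sends any subject whose creatinine clearance drops to 60 mL/min or lower to Table 6 in Section 5.5.6. The renal row there first interrupts lenalidomide for the rest of the cycle. It then instructs: "Reduce the dose of lenalidomide according to the recommendations below based upon creatinine clearance at the start of the next cycle". It also sets a floor: "Do not dose below 5 mg daily".

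For CrCl 30-60 mL/min the row has two branches, defined by the dose used when CrCl is above 60:

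- Where that dose "is 25 or 20 mg of lenalidomide, the starting dose is 10 mg every 24 hours".
- Where that dose "is 15 or 10 mg of lenalidomide, the starting dose is 5 mg" (no interval is printed).

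For CrCl <30 mL/min there is one line with no branches: "not requiring dialysis): 15 mg every 48 hours".

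A later bullet in the row rules out a lenalidomide increase unless the preceding cycle ran free of toxicity-related changes, holds or delays. It directly follows a bullet on stepwise titration for subjects started low because of baseline renal function.

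Table 7 lists stepwise reductions of 5 mg and has no renal tiers. Through it, a subject assigned 10, 15, 20 or 25 mg can reach 5 mg after one, two, three or four reductions. The SAP contains no dosing rule.

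**The concern.** A renal dosing rule should not give more drug as renal function worsens. The authors recognised that the renal dose has to depend on the assigned dose, since they split the 30-60 tier, but the next line was not split. At 15 and 10 mg, which are the Phase 1b doses of Cohorts 1, 1+ and -1, the more impaired tier therefore carries the larger dose, in a row whose instruction is to reduce.

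A site following the line as printed could raise lenalidomide in a subject on 5 mg daily at the moment CrCl falls below 30. CrCl is recalculated on Day 1 of every cycle, so the rule is consulted repeatedly. What is at stake is dosing safety in a small number of subjects, not the statistical analysis.

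**Working it through.** **Inputs.** Renal doses and the 5 mg floor: Protocol Table 6. Dosing on Days 1-21, then 7 days off: Section 5.5.4. Cohort doses: Table 4. Stepwise reductions: Table 7. The 5 mg line is read as daily, because the line above it says every 24 hours and the floor is stated per day.

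**Average daily dose** = dose ÷ interval in days.

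- CrCl <30, all subjects: 15 ÷ 2 = 7.5 mg/day.
- CrCl 30-60, assigned 25 or 20 mg: 10 ÷ 1 = 10 mg/day. Ratio 7.5 ÷ 10 = 0.75.
- CrCl 30-60, assigned 15 or 10 mg: 5 ÷ 1 = 5 mg/day. Ratio 7.5 ÷ 5 = 1.50.

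**Cycle total** = dose × number of doses in Days 1-21. Alternate-day dosing from Day 1 (Days 1, 3, ..., 21) gives 11 doses, 11 × 15 = 165 mg. From Day 2 it gives 10 doses, 10 × 15 = 150 mg. Daily dosing gives 21 × 10 = 210 mg or 21 × 5 = 105 mg.

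| Assigned dose | Full cycle (mg) | CrCl 30-60 (mg) | CrCl <30 (mg) | <30 vs 30-60 | <30 vs full dose |
|---|---|---|---|---|---|
| 25 mg | 525 | 210 | 150-165 | -29% to -21% | -71% to -69% |
| 20 mg | 420 | 210 | 150-165 | -29% to -21% | -64% to -61% |
| 15 mg | 315 | 105 | 150-165 | **+43% to +57%** | -52% to -48% |
| 10 mg | 210 | 105 | 150-165 | **+43% to +57%** | -29% to -21% |

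The order of the two renal tiers is right for 25 and 20 mg and inverted for 15 and 10 mg. Against the full assigned dose, the CrCl <30 dose is lower in every row. Each single 15 mg administration does exceed the assigned dose in the 10 mg cohort, and equals it in the 15 mg cohorts.

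**Subjects already on 5 mg daily under Table 7.** Applied literally, the unsplit line moves them from 5 to 7.5 mg/day, again a ratio of 1.50, whatever dose they were assigned.

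**Sensitivity to the missing interval.** If the 5 mg were every 48 hours (2.5 mg/day), the ratio would be 7.5 ÷ 2.5 = 3. The inversion does not depend on reading it as daily.

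**How many subjects.** Section 1.17 reports, as of 25 April 2016, subjects "in Cohort 1 (13 subjects enrolled, 12 treated), Cohort -1 (7 subjects enrolled), Cohort 1+ (9 subjects enrolled"). Treated at 10 or 15 mg: 12 + 7 + 9 = 28. Check: 37 treated in total minus 9 in Cohort 2 = 28. Of these, 7 were assigned 10 mg. The documents do not say how many subjects reached CrCl <30.

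**The case against.** The best defence is the row's own bullet on increases. A CrCl fall is listed in the toxicity column and triggers an interruption, so the preceding cycle was not free of holds. On a general reading, the move from 5 mg daily to 15 mg every 48 hours is then barred, and the instruction to reduce points the same way. This does not settle the matter. The bullet follows the titration bullet and can be read as governing only titration. If it is read generally, the row prescribes a dose that it also forbids, and names no other. A site would have two incompatible instructions.

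It is also fair to say that the consequence is small, and this stands. Inclusion criterion 8b required CrCl above 60 at entry. The review committee "unanimously voted to continue the study in Phase 1b with Cohort 3 (dose level of 25 mg of lenalidomide", and the sponsor planned to start the "Phase 2 portion of the study with the recommended Phase 2 dose of 20 mg lenalidomide", so later enrolment was planned at doses where the two tiers are in the right order.

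Third, no stated figure is miscalculated. That stands too: this is an inconsistency in a dosing table, not an arithmetic error.

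A reader might infer that subjects with severe renal impairment are dosed above their assigned level. The documents do not support that: on average they receive less than the full assigned dose in every cohort. A reader might also infer that the problem is confined to Cohorts -1, 1 and 1+, with 28 subjects as a ceiling. That fails as well, because Table 7 can bring a 20 or 25 mg subject to 5 mg, where the same line raises the dose.

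**Conclusion.** The CrCl <30 line is wrong as written, and nothing else in the protocol or SAP reliably corrects it. For assigned 15 or 10 mg it gives 50% more per day than the CrCl 30-60 tier (150-165 mg against 105 mg per cycle). Read literally, it produces the same 50% rise for any subject already on 5 mg daily. An actual increase for an individual needs that subject to be on 5 mg daily before falling below 30 mL/min. A fall directly from above 60 on the full assigned dose still lowers the average dose.

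Severity is minor. Few subjects are likely to be affected, though the number is not documented. The adjusted dose starts with the cycle after the CrCl fall, hence after the 28-day DLT window of Cycle 1, so DLT and MTD findings are unaffected. Sample size and the Phase 2 ORR analysis do not depend on this row.

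The conclusion assumes that the tiers are meant to step down with renal function, as the row's wording implies. The figures compare dose, not drug exposure.

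**What to change.** Amend the renal row of Table 6 as follows:

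1. Limit 15 mg every 48 hours to subjects assigned 25 or 20 mg.
2. For subjects assigned 15 or 10 mg, state that the CrCl <30 dose must not exceed the CrCl 30-60 dose: at most 5 mg every 24 hours, or hold or discontinue. Which of these applies is for the clinical team, because the 5 mg daily floor leaves no lower daily dose without an exception. The supplied 5 mg capsules can deliver the cap.
3. Add that a renal adjustment must never raise the subject's current average daily dose. Item 1 alone would leave 20 or 25 mg subjects already reduced to 5 mg uncorrected. This sentence covers them and removes the conflict with the bullet on increases.
4. Print every 24 hours on the 5 mg line.

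The cost is a short protocol clarification to one table row and notice to sites. Design, sample size and analysis do not change.
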